#### 2.10 Relapsed and/or Refractory Multiple Myeloma

The early development of ixazomib in patients with RRMM involves 2 studies (C16003 and C16004) with similar objectives, but each investigated 1 of the 2 dosing schedules commonly used with the first-in-class proteasome inhibitor, VELCADE.

Study C16003 is an open-label, dose escalation, phase 1 study of ixazomib dosing on a twiceweekly schedule on Days 1, 4, 8, and 11 of a 21-day cycle in adult patients with RRMM. Study C16004 is an open-label, dose escalation, phase 1 study of ixazomib dosing on a weekly schedule on Days 1, 8, and 15 of a 28-day cycle in adults patients with RRMM. Both studies have now completed enrollment. The DLTs in Study C16003 were rash macular and thrombocytopenia and the DLTs in C16004 were nausea, diarrhea, vomiting, and erythema multiforme.

In the dose escalation component of both studies, patients had multiple myeloma that had relapsed following at least 2 lines of therapy that must have included bortezomib, thalidomide (or lenalidomide), and corticosteroids. In both studies, when the MTD was established, cohorts of patients representing the heterogeneous patient population currently seen in clinical practice were to be enrolled into 1 of 4 expansion cohorts, including a relapsed and refractory cohort, a carfilzomib cohort, a proteasome inhibitor-naïve cohort, and a VELCADE-relapsed cohort.

Final study results are currently being analyzed, but preliminary data suggest that ixazomib has anti-tumor activity in heavily pretreated MM patients, with durable responses/disease control, and is generally well tolerated. Please refer to the ixazomib IB and SMA for further information.

### 2.11 Newly Diagnosed Multiple Myeloma (NDMM)

Multiple research paths are being explored in patients with NDMM with a focus on evaluating ixazomib in combination with agents commonly used across treatment settings. The development of ixazomib in combination with lenalidomide with dexamethasone (LenDex) in patients with NDMM who are transplant eligible or ineligible involves 2 studies (C16005 and C16008) with similar study designs except for a few key differences, namely the schedules of ixazomib and dexamethasone. Ixazomib is also being evaluated in combination with melphalan and prednisone (MP) for patients who are not transplant eligible due to age or coexisting morbidity (in Study C16006).

All 3 studies are phase 1/2, with phase 1 focusing on safety and phase 2 on efficacy (and further characterization of safety). Please refer to the ixazomib IB and SMA for further information.

### 2.12 Clinical Trial Experience Using the Intravenous Formulation of Ixazomib

See the IB for descriptions of the 2 studies that investigated IV ixazomib in advanced solid tumors and advanced lymphoma (Studies C16001 and C16002, respectively).

#### 2.13 Trial Rationale

Based on the activity of lenalidomide and dexamethasone in patients with SMM and based on the safety and activity profile of Ixazomib/len/dex in patients with untreated MM (ASH 2014), we propose to examine in a phase II trial the activity of ixazomib/lenalidomide/dexamethasone (IRD) in patients with high-risk smoldering MM.

Patients who develop symptomatic disease will receive induction therapy with standard therapeutic options for multiple myeloma including combinations such as those of proteasome inhibitors, immunomodulators and steroids or cyclophosphamide, proteasome inhibitors and dexamethasone.

Patients who are eligible for stem cell collection will have the option to collect stem cells during the course of therapy on this trial at the time of best response (CR or VGPR) or after 9 cycles of induction therapy. If we observe any problems with stem cell collection, we will follow the current standard guidelines of using cyclophosphamide or plerixafor mobilization. Based on data using combination therapies for induction, there has been no major concerns regarding stem cell collections after treatment with those agents.

#### 2.14 Potential Risks and Benefits

Please refer to the current ixazomib IB and SMA.

The clinical benefit of ixazomib continues to be studied in a comprehensive and global development plan that involves studies sponsored by Millennium. Ixazomib appears to show early signs of anti-tumor activity as evidenced by at least 50% reduction in disease burden in some patients, including patients that have been heavily pretreated as well as those with newly diagnosed MM, and prolongs stabilization of the underlying disease in other patients across all ongoing trials. The preliminary findings are favorable when considering historical and currently available therapies for the patient populations evaluated. Though additional data are needed to characterize the clinical benefit of this drug, the emerging data supports expanded development of ixazomib for the treatment of patients with advanced malignancy. This study will be conducted in compliance with the protocol, good clinical practice (GCP), applicable regulatory requirements, and International Conference on Harmonisation (ICH) guidelines.

#### 2.15 Correlative Studies Background

#### 2.15.1 DNA and RNA sequencing of tumor cells

The "clonal evolution" model of cancer emerged amid ongoing advances in technology, especially in recent years during which next generation sequencing has provided ever higher resolution pictures of the genetic changes in cancer cells and heterogeneity in tumors where tumor progression proceeds in a branching rather than in a linear manner, leading to substantial clonal diversity and coexistence of wide genetic heterogeneity. The genomic complexity in MM was recently corroborated by massive parallel-sequencing studies displaying the lack of a universal driving mutation. Recent studies have shown intraclonal heterogeneity that occurs at different stages of progression in MM. Most recently, exome sequencing confirmed that the heterogeneity observed in the transformation from MGUS/SMM to MM is likely to be an essential feature of clonal evolution and disease progression. Point mutations such as N-RAS, K-RAS, MYC up-regulation, and gain or loss of chromosome 1q or 1p seem to correlate with disease progression from MGUS and SMM. A progressive increase in the incidence of copy number abnormalities from MGUS to SMM and to MM has been recently observed.

We plan to perform exome sequencing and RNA sequencing studies on tumor cells obtained at the time of screening as well as from subsequent bone marrow biopsy samples to examine clonal heterogeneity, resistant clones at best response and at time of end of study or tumor progression.

The tumor research samples will be collected at the time of scheduled bone marrow biopsies. From these samples, high quality DNA (for tumor cells) and RNA for both exome sequencing and RNA sequencing will be obtained. In brief, BM aspirates will be obtained after informed consent. The tumor cells will be collected using CD138+ bead selection (over 90% purity based on prior publications). For samples that have a small fraction of plasma cells, we will use flow sorting for CD138/CD38/CD56 and CD19-ve to obtain a pure malignant plasma cell population based on prior published markers of malignant plasma cells. Germline DNA will also be obtained from a buccal swab from all patients.

Exome sequencing of tumor cells: Whole-exome capture libraries will be constructed from 100ng of tumor and normal DNA followed by shearing, end repair, phosphorylation and ligation to barcoded sequencing adapters. The DNA will be size-selected to exonic hybrid capture using SureSelect v2 Exome bait (Agilent, CA). Samples will be multiplexed and sequenced on Illumina HiSeq flowcells with the goal of an average depth of coverage of 100x. The resulting data will be analyzed with the current Illumina pipeline, which generates data files (BAM files). The details of the current analysis pipeline are published elsewhere. Briefly, somatic single nucleotide variants are determined using the MuTect algorithm^57. Indels and translocations are determined by the algorithms IndelLocator and dRanger, respectively. The MutSig algorithm identifies genes in which the observed mutations are inconsistent with what would be expected at random^58. To accurately assess the significance of mutations, MutSig takes into account several covariates, which influence the background mutation model. These include the expression level of genes (for which published gene expression data of MM samples can be used), and other gene characteristics observed empirically to co-vary with mutation rate: local relative replication time, and open vs. closed chromatin status. Focal as well as arm-level copy number variations will be determined based on whole exome sequencing and subsequent application of the GISTIC algorithm^61. All bioinformatics analysis will be performed by [name] and [name], who are expert Bioinformaticians and have analyzed the data shown in the preliminary data.

**RNA sequencing of tumor cells.** For RNA Sequencing, poly-A selection and cDNA synthesis will be performed, followed by library preparation, sequencing (76bp or 101bp paired reads), and sample identification with quality control. Details of experimental design are described in. We will perform library construction using a non-strand specific Illumina TruSeq Protocol and sequence coverage to 100M total reads. Analysis will be performed as described in the preliminary data and in previous studies.

**Single-cell sequencing of the tumor microenvironment.** Investigators at the Broad Institute and Harvard Medical School have recently developed the technology of droplet sequencing (Dropseq). In addition, multiple publications have shown that that single-cell RNA sequencing (RNA-seq) of the tumor microenvironment can define genotypic and phenotypic states of tumor cells and surrounding microenvironment, and that the microenvironment affected the gene expression program of tumor cells and their resistance to therapy. We will apply similar techniques in this study to evaluate the tumor microenvironment and assess specific changes in cell type and transcriptional signature of BM niche cells that correlate with tumor progression or resistance to therapy.

#### 3. PARTICIPANT SELECTION

#### 3.1 Eligibility Criteria

3.1.1 Age  $\geq$  18 years.

3.1.2 Must meet criteria of high-risk smoldering MM based on the criteria described below:

#### **Definition of high-risk SMM:**

- Bone marrow clonal plasma cells  $\geq 10\%$  and  $\leq 60\%$  and any one or more of the following:
  - Serum M protein  $\geq 3.0$ g/dL (IgA, IgG, IgM, or IgD)
  - IgA SMM
  - Immunoparesis with reduction of two uninvolved immunoglobulin isotypes
  - Serum involved/uninvolved free light chain ratio  $\ge$ 8 (but less than 100)
    - Free Light Chain Smoldering Myeloma patients as defined in section 2.4 are not excluded
  - Progressive increase in M protein level (Evolving type of SMM)
    - Increase in serum monoclonal protein by ≥10% on two successive evaluations within a 6-month period
  - Bone marrow clonal plasma cells 50-60%
  - Abnormal plasma cell immunophenotype (≥ 95% of bone marrow plasma cells are clonal) and reduction of one or more uninvolved immunoglobulin isotypes
  - $\circ$  t (4;14) or del 17p or 1q gain
  - Increased circulating plasma cells
  - MRI with diffuse abnormalities or 1 focal lesion
  - PET-CT with one focal lesion with increased uptake without underlying osteolytic bone destruction
  - Urine monoclonal light chain excretion  $\geq$  500 mg/24 hours
- 3.1.3 ECOG Performance Status (PS) 0, 1, or 2 (Appendix A)
- 3.1.4 The following laboratory values obtained  $\leq 21$  days prior to registration and confirmed prior to the first dose of study drug:
  - ANC  $\geq 1000/\mu L$
  - $PLT \ge 75,000/\mu L$ . Platelet transfusions to help patients meet eligibility criteria are not allowed within 3 days before study enrollment.
  - Total bilirubin ≤ 1.5 mg/dL (If total is elevated check direct and if normal patient is eligible.)
  - AST  $\leq$  3 x institutional upper limit of normal (ULN)
  - ALT  $\leq$  3 x institutional upper limit of normal (ULN)

#### CONFIDENTIAL

This document is confidential. Do not disclose or use except as authorized.

- Calculated creatinine clearance  $\geq$  30 mL/min
- 3.1.5 Ability to understand and the willingness to sign a written informed consent before performance of any study-related procedure not part of normal medical care, with the understanding that consent may be withdrawn by the subject at any time without prejudice to future medical care.
- 3.1.6 Female patients who are postmenopausal for at least 1 year before the screening visit or are surgically sterile. Females of childbearing potential\* must have a negative serum or urine pregnancy test with a sensitivity of at least 50 mIU/mL within 10 14 days and again within 24 hours prior to prescribing lenalidomide for Cycle 1 (prescriptions must be filled within 7 days as required by Revlimid REMS®) and must either commit to continued abstinence from heterosexual intercourse or begin TWO acceptable methods of birth control, one highly effective method and one additional effective method AT THE SAME TIME, at least 28 days before she starts taking lenalidomide. Female patients must agree to practice two effective methods of birth control from the time of signing the informed consent form though 90 days after the last dose of study drug
  - \* *A female of childbearing potential is a sexually mature female who:* 
    - Has not undergone a hysterectomy (the surgical removal of the uterus) or bilateral oophorectomy (the surgical removal of both ovaries) or
    - Has not been naturally postmenopausal (amenorrhea following cancer therapy does not rule out childbearing potential) for at least 24 consecutive months (i.e., has had menses at any time during the preceding 24 consecutive months)
- 3.1.7 All study participants must be registered into the mandatory Revlimid REMS® program, and be willing and able to comply with the requirements of the REMS® program.
- 3.1.8 Females of reproductive potential must adhere to the scheduled pregnancy testing as required in the Revlimid REMS® program.
- 3.1.9 Men must agree to use a latex condom during sexual contact with a female of childbearing potential even if they have had a successful vasectomy during the entire study treatment period and through *90 days* after the last dose of study drug OR agree to practice true abstinence when this is in line with the preferred and usual lifestyle of the subject. (Periodic abstinence (eg, calendar, ovulation, symptothermal, post-ovulation methods] and withdrawal are not acceptable methods of contraception.)

#### **3.2 Exclusion Criteria**

- 3.2.1 No evidence of CRAB\* criteria or new criteria of active MM which including the following:
  - Increased calcium levels (corrected serum calcium > 0.25 mmol/dL above the upper limit of normal or > 0.275 mmol/dL) related to MM
  - Renal insufficiency (attributable to MM)
  - Anemia (Hb 2g/dL below the lower limit of normal or <10g/dL) related to MM
  - Bone lesions (lytic lesions or generalized osteoporosis with compression fractures)
  - Bone marrow plasma cells > 60%
  - Serum involved/uninvolved FLC ratio ≥ 100, provided the absolute level of the involved free light chain is at least 100 mg/L and repeated twice
  - MRI with two or more focal lesion that is at least 5 mm or greater in size

\*Participants with CRAB criteria that are attributable to conditions other than the disease under study may be eligible

- 3.2.2 Other concurrent chemotherapy, immunotherapy, radiotherapy, or any ancillary therapy considered investigational. Prior therapy with bisphosphonate is allowed. Prior radiation therapy to a solitary plasmacytoma is allowed.
- 3.2.3 Serious medical or psychiatric illness likely to interfere with participation in this clinical study.
- 3.2.4 Diagnosed or treated for another malignancy within 2 years of enrollment, with the exception of complete resection of basal cell carcinoma or squamous cell carcinoma of the skin, an in situ malignancy, or low-risk prostate cancer after curative therapy.
- 3.2.5 Uncontrolled intercurrent illness including, but not limited to, ongoing or active infection, symptomatic congestive heart failure, unstable angina pectoris, cardiac arrhythmia, or psychiatric illness/social situations that would limit compliance with study requirements.
- 3.2.6 Pregnant or nursing women will be excluded from the study because lenalidomide is an agent with the potential for teratogenic or abortifacient effects.
- 3.2.7 History of allergic reactions attributed to compounds of similar chemical or biologic composition to ixazomib or lenalidomide.

- 3.2.8 Known seropositive for or active viral infection with human immunodeficiency virus (HIV), hepatitis B virus (HBV) or hepatitis C virus (HCV). Patients who are seropositive because of hepatitis B virus vaccine are eligible.
- 3.2.9 Major surgery within 14 days before first dose of ixazomib.
- 3.2.10 Known Amyloid involvement.
- 3.2.11 Myeloma-related central nervous system involvement.
- 3.2.12 Systemic treatment, within 14 days before the first dose of ixazomib with strong CYP3A inducers (rifampin, rifapentine, rifabutin, carbamazepine, phenytoin, phenobarbital), or use of Ginkgo biloba or St. John's wort.
- 3.2.13 Known GI disease or GI procedure that could interfere with the oral absorption or tolerance of ixazomib including difficulty swallowing.
- 3.2.14 Grade 2 peripheral neuropathy or higher or grade 1 with pain on clinical examination during the screening period.
- 3.2.15 Participation in other clinical trials, including those with other investigational agents not included in this trial, within 30 days of the start of this trial and throughout the duration of this trial.
- 3.2.16 Previous treatment with ixazomib, or participation in a study with ixazomib whether treated with ixazomib or not.

#### **3.3** Inclusion of Women and Minorities

3.3.1 Both men and women of all races and ethnic groups are eligible for this trial.

#### 4. REGISTRATION PROCEDURES

#### 4.1 General Guidelines for DF/HCC Institutions

Institutions will register eligible participants in the Clinical Trials Management System (CTMS) OnCore. Registrations must occur prior to the initiation of protocol therapy. Any participant not registered to the protocol before protocol therapy begins will be considered ineligible and registration will be denied.

An investigator will confirm eligibility criteria and a member of the study team will complete the protocol-specific eligibility checklist.

Following registration, participants may begin protocol therapy. Issues that would cause treatment delays should be discussed with the Overall Principal Investigator (PI). If a participant does not receive protocol therapy following registration, the subject must be taken off-study in
the CTMS (OnCore) with an appropriate date and reason entered.

#### 4.2 Registration Process for DF/HCC Institutions

DF/HCC Standard Operating Procedure for Human Subject Research Titled *Subject Protocol Registration* (SOP #: REGIST-101) must be followed.

#### 4.3 General Guidelines for Other Investigative Sites

Eligible participants will be entered on study centrally at DFCI by the Project Manager. All sites should call the Project Manager to verify study status and slot availability.

Following registration, participants should begin protocol therapy as soon as feasible. Issues that would cause treatment delays should be discussed with the Overall PI. If a participant does not receive protocol therapy following registration, the participant's registration on the study must be canceled. The Project Manager should be notified of cancellations as soon as possible.

#### 4.4 Registration Process for Other Investigative Sites

To register a participant, the following documents should be completed by the research nurse or data manager and e-mailed to the Research Project Manager:

- Copy of labs and clinical information that satisfy inclusion criteria
- Signed participant consent form
- HIPAA authorization form
- Registration Form

The research nurse or data manager at the participating site will then call or e-mail

the Research Project Manager, to verify eligibility. To complete the registration process, the Coordinator will follow DF/HCC Standard Operating Procedure for Human Subject Research Titled *Subject Protocol Registration* (SOP #: REGIST-101) and register the participant on the protocol. The coordinator will fax or e-mail the participant study number, and if applicable the dose treatment level, to the participating site. The coordinator will also call the research nurse or data manager at the participating site and verbally confirm registration

## Treatment may not begin without confirmation from the Coordinating Center that the participant has been registered.

### NOTE: Same day treatment registrations will only be accepted with prior notice and discussion with DFCI.

#### 5. TREATMENT PLAN

#### 5.1 Treatment Regimen

Treatment will consist of 9 cycles of induction therapy followed by maintenance therapy for a total of 24 months. A treatment cycle is defined as 28 consecutive days.

For treatments cycle 1 and 2, a +/- 3 day window is allowed. For treatments cycle 3 through 24 a +/-7 day window is allowed.

No investigational or commercial agents or therapies other than those described below may be administered with the intent to treat the participant's malignancy.

| Agent         | Pre-medications/
Precautions                              | Dose  | Route | Schedule                   | Cycle
Length |
|---------------|--|-------|-------|----------------------------|-----------------|
| Ixazomib      | Should not be taken with food                                | 4 mg  | Oral  | Days 1, 8, 15              |                 |
| Lenalidomide  | None   | 25 mg | Oral  | Days 1–21 of
each cycle | 28 days         |
| Dexamethasone | Take with food;
Recommended to be
taken in the morning | 40 mg | Oral  | Days 1, 8, 15, 22          | -               |

#### **Induction Cycles**

#### **Maintenance Cycles**

| Table 8: Ixazomib and Lenalidomide Combination (Cycles 10-24)† |                                  |         |       |                            |                 |
|--|----------------------------------|---------|-------|----------------------------|-----------------|
| Agent  | Pre-medications/
Precautions  | Dose    | Route | Schedule                   | Cycle
Length |
| Ixazomib   | Should not be taken
with food | 4 mg*   | Oral  | Days 1,8, 15               | 29 dava         |
| Lenalidomide   | None                             | 15 mg** | Oral  | Days 1–21 of
each cycle | 28 days         |

\* If patient was dose reduced during the induction phase for ixazomib below 4mg, then maintenance phase starts at that dose reduction and not at the higher 4 mg dose.

\*\* If patient was dose reduced during the induction phase for lenalidomide below 15mg, then maintenance phase starts at that dose reduction and not at the higher 15 mg dose.

†After discussion with the overall principal investigator, high-dose dexamethasone may be readded during maintenance due to biochemical progression (progressive increase in SPEP [25% and an absolute increase of 0.5g/dL] or UPEP [25% and an absolute increase of 200mg/24hours] on 2 successive evaluations as determined by the IMWG response criteria or documented progression by the FreeLiteTM progressive disease criteria in the absence of serum or urine

involvement). If approved by the overall PI, dexamethasone should be given as an oral dose of 40mg on days 1, 8, 15, and 22.

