#### 5.2.3 **Dexamethasone**

Dexamethasone will be obtained from commercial supply in this study. This may lead to added costs for the participant or the participant's insurance company.

Dexamethasone will be given as a single oral dose on days 1, 8, 15, and 22 of each 28 day cycle during the induction phase of this study (Cycles 1-9 only).

Dexamethasone should be taken at approximately the same time each day. It is recommended that dexamethasone be taken in the morning to reduce insomnia. Each dose should be taken with food. If a dose of dexamethasone is vomited, the participant should continue with the regular schedule of the drug at the next dose. If a dose is missed and less than 12 hours has elapsed since the missed dose, the patient may take the dose for that day. If more than 12 hours has elapsed since missing a dose at the normal time, the patient should not take the dose, but take the next dose at the normal time on the following day. A drug diary will be provided to participants to record oral administration of doses.

At the treating investigator's discretion, dexamethasone may be given as a split dose over 2 consecutive days.

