#### If lenalidomide is reduced for any toxicity, the dose may not be re-escalated.

#### 6.3 Dexamethasone

|   | Dose Modificati   |   |
|---|---|---|
|   | Gast  | rointestinal  |
| Dyspepsia   | Grade 1-2   | Treat with H2 blockers, sucralfate, or omeprazole.
If symptoms persist despite above measures,
decrease dexamethasone by 1 dose level   |
| Gastric or
Duodenal Ulcer
Gastritis   | ≥ Grade 3
(requiring
hospitalization
or surgery) | Hold dexamethasone until symptoms adequate
controlled. Restart and decrease 1 dose level of
current dose along with concurrent therapy with
H2 blockers, sucralfate, or omeprazole. If
symptoms persist despite above measures, |
|   |   | discontinue dexamethasone and do not resume.  |
| Acute Pancreatitis  | All Grades  | Discontinue dexamethasone and do not resume.  |
|   | Care  | diovascular   |
| Edema   |   | Diuretics as needed, and decrease dexamethasone dose by 1 dose level;   |
| (limiting function and
unresponsive to therapy or
anasarca)   | $\geq$ Grade 3  | If edema persists despite above measures, decrease
dose another level and do not resume if symptoms
persist despite second reduction.   |
|   | N   | eurology  |
| Confusion or Mood
Alterations
(interfering with function
+/- interfering with
estimities of daily living)   | $\geq$ Grade 2  | Hold dexamethasone until symptoms resolve.
Restart with 1 dose level reductions.
If symptoms persist despite above measures,
discontinue dexamethasone and do not resume.  |
| activities of daily living)   |   |   |
|   | Muse  | culoskeletal  |
| Muscle Weakness
(symptomatic and
interfering with function
+/- interfering with
activities of daily living) | ≥ Grade 2   | Decrease dexamethasone 1 dose lever.
If weakness persists despite above measures
decrease by 1 dose level.
Discontinue dexamethasone and do not resume if
symptoms persist.   |
|   | N   | letabolic   |
| Hyperglycemia   | ≥ Grade 3   | Treatment with insulin or oral hypoglycemics as
needed.
If uncontrolled despite above measures, decrease
dose level by 1 dose level until levels are
satisfactory.  |

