#### Table 14: Dexamethasone Dose Modifications

If the patient discontinues dexamethasone, he or she does not need to come off protocol therapy.

| Table 15: | Dexamethasone | dose reduction |
|-----------|---------------|----------------|
|-----------|---------------|----------------|

| Dose Level | Dexamethasone Dose |
|------------|--------------------|
| 0          | 40 mg              |
| -1         | 20 mg              |
| -2         | 10 mg              |

If dexamethasone is reduced for any toxicity, the dose may not be re-escalated.

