#### 8.3.7 Administration

During induction therapy, participants will receive dexamethasone as a single oral daily dose on Days 1, 8 and 15 and 22 of cycles 1-9.

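### The Table 8 dagger footnote restarts dexamethasone at a fixed 40 mg in maintenance and does not carry forward the induction reductions and stops that Section 6.3 protects

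*Combined protocol and SAP*

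**What the plan says.** Table 8 (Section 5.1, Maintenance Cycles) lists ixazomib and lenalidomide for cycles 10–24. Dexamethasone is not a row in it. The dagger footnote allows dexamethasone to come back when there is biochemical progression, after discussion with the overall PI, and then fixes the dose: "If approved by the overall PI, dexamethasone should be given as an oral dose of 40mg on days 1, 8, 15, and 22". It gives no lower dose, does not refer to Section 6.3, and does not mention what happened to the drug in induction.

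The two footnotes beside it do look back at induction. For ixazomib: "If patient was dose reduced during the induction phase for ixazomib below 4mg, then maintenance phase starts at that dose reduction". For lenalidomide: "If patient was dose reduced during the induction phase for lenalidomide below 15mg, then maintenance phase starts at that dose reduction".

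Section 6.3 sets the dexamethasone rules. Table 15 has three levels: 40, 20 and 10 mg. The text with it says: "If dexamethasone is reduced for any toxicity, the dose may not be re-escalated". For acute pancreatitis of any grade, Table 14 requires the drug to be stopped for good. The ulcer/gastritis row, if symptoms persist, says: "discontinue dexamethasone and do not resume". The rows for edema, confusion or mood alteration, and muscle weakness also bar resumption if symptoms persist. Stopping the drug does not end participation: "If the patient discontinues dexamethasone, he or she does not need to come off protocol therapy".

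The other dosing text covers induction only. Section 8.3.7 begins "During induction therapy, participants will receive dexamethasone as a single oral daily dose", and Section 5.2.3 likewise limits dosing to cycles 1–9.

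**The concern.** A patient can be reduced to 20 or 10 mg in induction, or stop dexamethasone altogether, continue on the other two drugs into maintenance, and then progress biochemically. The dagger footnote is the only text that gives a dose for that moment, and the dose is 40 mg, the level this patient has already failed to tolerate. Because the neighbouring footnotes restate the carry-forward for drugs that already have their own no-re-escalation rule, its absence for dexamethasone looks like an oversight. It could be taken to mean that induction history does not count.

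What is at stake is the safety of individual patients, not the statistical design. It is also unstated whether restarting at 40 mg after months without the drug counts as re-escalation.

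**Working it through.** There is no planned figure to reproduce. The check sets the footnote beside Section 6.3 for each possible induction history.

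Inputs: restart dose 40 mg on days 1, 8, 15 and 22, so 4 doses per 28-day cycle (dagger footnote); reduced levels 20 and 10 mg (Table 15); no re-escalation, and the stop instructions (Section 6.3, Table 14).

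Dose per cycle = 4 × single dose: 4 × 40 = 160 mg; 4 × 20 = 80 mg; 4 × 10 = 40 mg.

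| Induction history | Dagger read alone | Section 6.3 | Difference |
|---|---|---|---|
| Never reduced | 40 mg (160 mg per cycle) | 40 mg (160 mg) | none |
| Reduced to 20 mg for toxicity | 40 mg (160 mg) | at most 20 mg (80 mg) | 40/20 = 2 times |
| Reduced to 10 mg for toxicity | 40 mg (160 mg) | at most 10 mg (40 mg) | 40/10 = 4 times |
| Stopped under a do-not-resume instruction | 40 mg (160 mg) | none | drug restarted against 6.3 |

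Three further questions follow.

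1. Can these patients reach the point where the footnote applies? Yes. Reduced patients continue at the lower dose, and Section 6.3 says that stopping dexamethasone need not end protocol therapy.
2. How wide is the bar on resumption? Table 14 has seven toxicity rows. One (acute pancreatitis) bars resumption unconditionally. Four (ulcer/gastritis, edema, confusion or mood alteration, muscle weakness) bar it only if symptoms persist after the measures listed. Two (dyspepsia, hyperglycemia) do not bar it.
3. Does any other text reconcile the two rules? Section 5.2.3.1 points to 6.3 for dexamethasone modifications, which favours 6.3. Neither the footnote nor 6.3 says which prevails on a restart.

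The documents give no rate of dexamethasone reduction, stopping or re-adding, so the number of patients affected cannot be calculated.

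**The case against.** The strongest reply is that Section 5 gives nominal doses and Section 6 modifies them. The induction table also shows a bare 40 mg on the same four days, and nobody would read it as cancelling Table 15. Section 6.3 is not tied to a treatment phase, and nothing in the dagger footnote displaces it. On this reading there is no conflict, only a missing cross-reference. This largely stands. A reader might infer that the plan authorises 40 mg in spite of 6.3, but the documents do not say so.

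Second, the contrast with the other two footnotes has an innocent explanation. Ixazomib and lenalidomide continue into cycle 10 by default, and lenalidomide moves to a new nominal dose, so a carry-forward note is needed there. Dexamethasone returns only as an approved exception. This is fair, and it weakens the inference from silence. It does not supply the missing dose for a reduced patient.

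Third, one overall PI must discuss and approve every restart. This is a real safeguard. A reader might infer that different sites would dose the same patient differently; with a single approver that inference is not well supported. It might also be argued that the PI may decide only whether to restart, because the sentence in Section 6.1 on discussing modifications with the PI names only ixazomib and lenalidomide. That sentence sits in the ixazomib section, and its silence does not prevent a discussion of dexamethasone. What remains is that the footnote makes approval the condition for 40 mg, names no alternative dose, and does not prompt a check of toxicity history.

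**Conclusion.** The point holds as a modest, safety-related wording defect. Applied as written to a patient who was reduced for toxicity, or stopped under a do-not-resume instruction, the footnote gives a dose that Section 6.3 forbids: 2 or 4 times the permitted dose, or a restart where none is allowed. This rests on reading the footnote literally and on treating a restart above the last reduced dose as re-escalation. Both readings are reasonable; neither is stated. For patients who were never reduced or stopped, the two texts agree.

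Two larger claims should not be drawn from this. A reader might try to estimate how many of the 56 patients would be affected, but any such figure would rest on assumed shares, and the true number may be zero. A reader might also add up the excess dose over all of maintenance. That would require a restart at cycle 10 and full dosing to cycle 24 with no further reduction, which the documents give no reason to expect.

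**What to change.** Replace the last sentence of the dagger footnote with wording to this effect:

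> With the overall PI's approval, dexamethasone is given orally on days 1, 8, 15 and 22 at 40 mg or, where it was reduced for toxicity during induction, at the last reduced dose (Table 15). It is not re-added in a patient whose dexamethasone was stopped under a do-not-resume instruction in Table 14.

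This applies the existing 6.3 rule and matches the treatment of the other two drugs. A pointer from Sections 5.2.3 and 8.3.7 to the footnote would be optional housekeeping.

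The cost is one wording amendment, with no added patients, visits or tests. Section 8.3.2 lists 2 mg and 4 mg tablets, which cover the reduced doses (5 × 4 = 20 mg; 5 × 2 = 10 mg). The downside is that a previously reduced patient receives less than 40 mg at biochemical progression, but Section 6.3 already requires that.
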